1.3.1. Known and Potential Benefits and Risks of the Test Investigational Medicinal Product(s)

Results from Phase 2b clinical studies have demonstrated statistically significant reductions in mean headache hours after 1, 2, and 3 months of sc fremanezumab treatment in patients with chronic migraine and statistically significant reductions in monthly migraine days after 1, 2, and 3 months of fremanezumab treatment in patients with episodic migraine. Results for several secondary/exploratory endpoints also showed fremanezumab to be superior to placebo.

Fremanezumab has generally been well tolerated over the ranges of doses evaluated (single iv infusions at 0.02 to 2000 mg in healthy subjects, multiple iv infusions at 30 to 300 mg in healthy subjects, and multiple sc doses at 225 to 900 mg in healthy subjects and migraine patients). The most common treatment-emergent adverse events across all patients/subjects studied were mild to moderate transient general administration site disorders/reactions. Other commonly reported treatment-emergent adverse events were headache, back pain, and upper respiratory tract infection.

Reports of mild to moderate transient administration site disorders/reactions, including injection site bruising, injection site swelling, administration site pain, injection site pain, injection site pruritus, injection site dermatitis, injection site rash, injection site edema, injection site discomfort, injection site hemorrhage, injection site irritation, injection site mass, and injection site hematoma, have occurred with sc administration. In addition, reports of mild and transient infusion site pain and swelling following iv administration have occurred. Among these events, the following have been identified as adverse drug reactions (identified risks): injection site erythema, administration site pain, injection site pain, injection site pruritus, and injection site dermatitis. None of these identified risks are considered important risks.

Infusion-related reaction and drug hypersensitivity were also identified as adverse drug reactions. To date, 1 subject who received fremanezumab iv had a non-serious infusion-related reaction, and 1 patient who received fremanezumab via the sc route had a non-serious event of drug hypersensitivity. Both events resolved following IMP discontinuation and treatment with diphenhydramine and methylprednisolone. Neither of these identified risks are considered important risks.

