4.3. Withdrawal Criteria and Procedures

Each patient is free to withdraw from the IMP and/or study at any time, without prejudice to their continued care. Patients must be withdrawn from the IMP and/or study if any of the following events occur:

1. Patient withdraws consent or requests discontinuation from the IMP and/or study for any reason.
2. Patient develops an illness that would interfere with his/her continued participation.
3. Patient is noncompliant with the study procedures and assessments or administration of IMPs in the opinion of the investigator.
4. Patient takes prohibited concomitant medications as defined.
5. A female patient has a confirmation of pregnancy during the study from a positive pregnancy test.
6. The sponsor requests withdrawal of the patient.
7. Patient experiences an adverse event or other medical condition which indicates to the investigator that continued participation is not in the best interest of the patient.
8. The investigator and/or sponsor may withdraw an individual patient from the study at any time for any reason (eg, lack of efficacy, protocol deviation as defined in Section 10, noncompliance, or adverse event). In addition, patients with positive eC-SSRS findings or abnormal hepatic laboratory values (eg, ALT, AST, ALP, GGT, bilirubin [total, direct, or indirect], or INR) may meet criteria for discontinuation from the IMP as summarized in [Appendix J](#).

In the event that a patient was incorrectly randomized and has already started taking the study drug, a risk/benefit evaluation should take place between the investigator and sponsor and a strong clinical justification must be provided if the patient is not withdrawn from study drug.

Patients should be treated with standard of care after withdrawal from or termination of the study as appropriate.

Investigators should attempt to obtain information on patients in the case of withdrawal or discontinuation. Results of any evaluations and observations, together with a narrative describing the reason(s) for withdrawal, must be recorded in the source documents. The case report form (CRF) must document the primary reason for withdrawal or discontinuation.

See [Appendix F](#) for information regarding how the study will define and address lost to follow-up patients to help limit the amount and impact of missing data.

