If a patient is withdrawn from the study for multiple reasons that include also adverse events, the termination page of the CRF should indicate that the withdrawal was related to an adverse event.

An exception to this requirement will be the occurrence of an adverse event that in the opinion of the investigator is not severe enough to warrant discontinuation but that requires the use of a prohibited medication, thereby requiring discontinuation of the patient. In such a case, the reason for discontinuation would be “need to take a prohibited medication” and not the adverse event.

Should a patient decide to withdraw after administration of the IMP or should the investigator decide to withdraw the patient, all efforts will be made to complete and report all observations up to the time of withdrawal. A complete final evaluation at the time of the patient’s withdrawal should be made and an explanation given as to why the patient is withdrawing or being withdrawn from the study.

The reason for and date of withdrawal from the study must be recorded on the source documentation and transcribed to the CRF. If a patient withdraws consent, every attempt will be made to determine the reason.

All protocol-specified procedures/assessments should be performed at the early withdrawal visit (see [Appendix B](#)). Patients who withdraw from the study will not be replaced. Patients who discontinue early for any reason will be offered the opportunity to enter in the long-term safety study (Study TV48125-CNS-30058) for the purpose of evaluation of ADAs and safety (adverse events and concomitant medications) approximately 7.5 months after administration of the last dose of IMP in this study. These patients will not receive any doses of fremanezumab after completing participation in the current study and should be treated with standard of care as appropriate.

A patient should only be designated as lost to follow up if the site is unable to establish contact with the patient after 3 documented attempts via 2 different methods (phone, text, e-mail, certified letter, etc). In the case of patients lost to follow-up, attempts to contact the patient must be made and documented in the patient’s medical records and transcribed to the CRF.

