APPENDIX H. PREVENTIVE CLUSTER HEADACHE MEDICATIONS AND DISALLOWED MEDICATIONS

1. Medications Commonly Prescribed for Cluster Headache

The following medications will be considered as being used for the prevention of cluster headaches, regardless of the initial indication.

- verapamil
- lithium
- methysergide
- valproate
- topiramate

Patients are allowed to take up to 2 of these medications provided that they are on a stable dose and regimen for at least 2 weeks prior to screening and throughout the study.

If a patient is receiving Botox, it should be in a stable dose regimen, considered as having ≥ 2 cycles of Botox prior to screening. The patient should not receive Botox during the run-in period up to the evaluation period (4 weeks) where the primary endpoint is evaluated.

2. Concomitant Medications Allowed and Disallowed

Steroids:

Screening/run-in period and throughout the study: Systemic steroids are not allowed to be used in the treatment of cluster cycles during the screening/run-in period and for the duration of the study.

The only allowed steroids are intra-articular injection or ocular, ear drops, intranasal, inhaled, and creams for topical use.

Screening/run-in period: Disallowed if patient has used systemic steroids for any medical reason (including treatment of the current CH cycle) within ≤ 7 days of screening.

Butalbital:

Screening/run-in period: Disallowed if used more than 3 days during the screening/run-in period. Patients can use butalbital as needed (PRN) after randomization into the study.

Opioids:

Screening/run-in period: Disallowed if used more than 4 days during the screening/run-in period. Patients can use opioids PRN after randomization into the study.

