8.3. Adverse Events

Adverse events will be recorded from time informed consent is obtained through the end of study participation.

The following are considered protocol-defined adverse events of special interest to be sent to the sponsor's Global Patient Safety and Pharmacovigilance Department for evaluation: ophthalmic-related adverse events of at least moderate severity, events of possible drug-induced liver injury (aspartate aminotransferase or alanine aminotransferase $\geq 3 \times$ the upper limit of normal [ULN], total bilirubin $\geq 2 \times$ the ULN, or international normalized ratio >1.5), Hy's Law events, or events of anaphylaxis and severe hypersensitivity reactions.

All adverse events will be coded using MedDRA (version 18.1). Each patient will be counted only once in each preferred term or SOC category for the analyses of safety. Summaries will be presented for all adverse events (overall and by severity), adverse events determined by the investigator to be related to test IMP (defined as related or with missing relationship) (overall and by severity), serious adverse events, and adverse events causing withdrawal from the study. Adverse events with the missing flag indicating serious will be excluded from the summary of serious adverse events but included in the summary of non-serious adverse events.

Summaries for injection site and infusion-related adverse events and protocol-defined adverse events of special interest will be presented (overall and by severity).

Listings for deaths, serious adverse events, adverse events leading to discontinuation, injection site and infusion-related adverse events, and protocol-defined adverse events of special interest will be presented. In addition, listings for MedDRA dictionary terms for adverse event descriptions and adverse event preferred terms by patient number and treatment group will be presented.

Spontaneous abortion or an elective abortion due to developmental anomalies will be reported as a serious adverse event (protocol Section 7.2). These serious adverse events will be listed separately if applicable.

Summaries will include treatment-emergent adverse events which are defined as adverse events occurring at or after the first dose of the IMP. The listing will include all adverse events recorded.

Adverse events for patients who did not meet screening criteria will be listed.

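### Protocol Section 4.3 records a withdrawal under the prohibited drug, not the adverse event that made the drug necessary, so withdrawal tables can misattribute or undercount it

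*Protocol*

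**What the plan says.** Protocol Section 4.3 gives a general rule and an exception.

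- **Rule.** If a patient withdraws for several reasons and one is an adverse event, "the termination page of the CRF should indicate that the withdrawal was related to an adverse event".
- **Exception.** This covers an event that the investigator considers "is not severe enough to warrant discontinuation but that requires the use of a prohibited medication, thereby requiring discontinuation of the patient". The text continues: "In such a case, the reason for discontinuation would be" the need for the prohibited drug, and it expressly rules out the adverse event as the reason.

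The same section lists, among the events for which a patient must be withdrawn, "Patient takes prohibited concomitant medications as defined".

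Two outputs depend on how withdrawals are attributed. Protocol 9.4.1 and SAP 5.2 tabulate withdrawals by reason. Protocol 9.7 and SAP 8.3 plan summaries that include "serious adverse events, and adverse events causing withdrawal from the study". Protocol 7.1.2 also requires the action taken with study drug to be recorded for each adverse event. The readable text of the SAP does not say which of these records feeds the adverse-event withdrawal table.

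**The concern.** In the situation the exception describes, the adverse event starts the chain: the event needs the drug, and the drug ends participation. The general rule would attribute that withdrawal to the event. The exception attributes it to the drug alone, and nothing readable in the SAP adds the patient back.

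Adverse events that lead to withdrawal are a standard measure of how well a treatment is tolerated. Both documents say that tolerability has no separate definition here, so this count carries more weight. A convention that can only lower it deserves a second look.

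The exception could touch reactions the protocol already links to the product. Protocol 1.3.1 reports one infusion-related reaction after iv dosing and one drug hypersensitivity after sc dosing, both non-serious: "Both events resolved following IMP discontinuation and treatment with diphenhydramine and methylprednisolone". Methylprednisolone is a systemic steroid, and Appendix H says: "The only allowed steroids are intra-articular injection or ocular, ear drops, intranasal, inhaled, and creams for topical use". A comparable reaction in this trial, treated the same way but judged not to warrant stopping in itself, could fall under the exception.

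**Working it through.** The plan states no figure on this point, so there is none to reproduce. The check sets the texts side by side and then estimates scale.

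**Which withdrawals are recoded**

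| Situation | Recorded reason under Section 4.3 |
|---|---|
| Event judged to warrant stopping | Adverse event |
| Several reasons, one an adverse event | Adverse event |
| Event judged not to warrant stopping, needs a prohibited drug, patient discontinued for that | Prohibited drug |

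Only the third row is affected.

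**What happens in each table**

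1. Disposition by reason (Protocol 9.4.1, SAP 5.2): the patient appears under the drug whenever the exception is used.
2. Adverse events causing withdrawal (Protocol 9.7, SAP 8.3), built from the termination page: the patient is missing.
3. The same table built from the action-taken entry (Protocol 7.1.2): the patient can appear, and the table can then disagree with disposition.

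**How many patients**

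Inputs: 2 reactions treated with a systemic steroid (Protocol 1.3.1); 484 subjects or patients exposed in completed studies (Protocol 1.2.2); about 100 patients per group, so about 200 on active drug (Protocol 3.2). It is assumed that both reactions fall within the 484.

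- Rate: 2 / 484 = 0.41%.
- Expected among 200: 200 × 2/484 = 0.83.
- Chance of at least one: 1 − (1 − 2/484)^200 = 0.56.
- Chance of two or more: about 0.20.

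At that rate, these are upper bounds on recoding from the two kinds of reaction, because not every such case would be judged too mild to stop for. If the rate of such reactions were 1% or 2% (assumed), the expected numbers would be 2 and 4, and the chances of at least one 87% and 98%. Other adverse events needing a prohibited drug would add to this; the documents give no figure for them.

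**Effect of one recoded patient**

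- On an arm's rate: 1 / 100 = 1 percentage point.
- On an arm's count, if it truly has 2 to 5 adverse-event withdrawals (assumed): 1/5 = 20% to 1/2 = 50%.

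**The case against.** The strongest reply is that this is a deliberate coding convention with a narrow trigger and little consequence. Most of its parts stand as limits.

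- **Narrow scope.** A reader might infer that any adverse-event withdrawal involving a prohibited drug is recoded. It is not: an event that itself warrants stopping keeps its coding.
- **The two earlier reactions are not examples.** A reader might infer that they would have been recoded. Study drug was stopped in both as part of management, and nothing shows that either was thought not to warrant stopping. The 2/484 rate therefore counts steroid-treated reactions, not recodable ones. Its denominator is also uncertain, since 484 covers completed studies while the reactions are counted to date, with five studies ongoing.
- **No event is lost.** A reader might infer that hypersensitivity reactions disappear from the safety report. They do not. SAP 8.3 summarises all adverse events, with separate summaries for infusion-related events and for events of special interest, which include anaphylaxis and severe hypersensitivity. SAP 8.5 summarises suspected anaphylaxis, and SAP 8.12 tabulates concomitant drugs. Mild or moderate hypersensitivity after sc dosing has the least dedicated coverage, but it is still in the general tables.
- **No proven bias between arms.** A reader might infer that the exception works selectively on the active groups. It applies to any event in any arm, under blinding.
- **Withdrawal may not follow.** Protocol 7.1.8 leaves continuation after an adverse-event deviation to the investigator in consultation with the sponsor, and Appendix C lets the sponsor permit a patient with an important deviation to continue.
- **The trigger is unclear.** Appendix H also says "Systemic steroids are not allowed to be used in the treatment of cluster cycles", which ties the ban to one indication, whereas the list of allowed routes is not so limited.

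The reply does not explain why, when the exception does apply, the adverse event should be left out of the recorded reason, nor does it supply the missing definition in the SAP.

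**Conclusion.** The point holds in limited form. As written, the plan misattributes a defined type of withdrawal in the disposition table. It either undercounts that type in the adverse-event withdrawal table or lets the two tables disagree, depending on a data source the documents do not state.

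The likely size is small: at the earlier rate, fewer than one patient expected across the two active groups. That rests on 2/484 carrying over to this trial and on every such case being recoded, which overstates it. No documented case meets the exception. Even so, with about 100 patients per arm and few adverse-event withdrawals, a single patient would be visible in the table.

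This is a worthwhile, inexpensive correction to reporting. It is not evidence that safety events are hidden.

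**What to change.** 1. **Protocol 4.3 and CRF completion guidance.** Remove the exception. The termination page then records the adverse event as the reason, with the prohibited drug as a linked secondary reason.
2. **SAP 8.3.** Define adverse events causing withdrawal to include any event whose treatment required the prohibited drug that led to withdrawal. Show these by arm and name the data field used, so that the table agrees with SAP 5.2.
3. **Separately, reconcile the text on prohibited steroids.** Appendix H contains one sentence limited to cluster cycles and one that is not. Protocol 7.10 refers to Section 5.6 for details of prohibited drugs, but Section 5.6 lists none. Which rule should apply is for the sponsor to settle.

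Items 1 and 2 cost one sentence in the protocol, a change to the CRF guidance and about one line in the SAP. They change no treatment or stopping rule. The one downside is that the reported adverse-event withdrawal rate may be slightly higher.

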4.4. Replacement of Patients

A patient who is randomized/enrolled but does not complete the treatment period will not be replaced with another eligible patient.

4.5. Rescreening

A patient who is screened and does not meet study inclusion and exclusion criteria will not be considered for screening again, except for patients who do not meet study inclusion criterion “h” of the required number of cluster attacks during run-in period. These patients may be eligible for one additional rescreening if approved by the sponsor on a case-by-case basis.

4.6. Screening Failure

Screening failures are defined as participants who consent to participate in the clinical study but are not subsequently randomized/enrolled in the study. Minimal information includes but is not limited to demography, screening failure details, eligibility criteria, and any adverse events or serious adverse events.

previous injection sites to ensure that they are free of bruising and tenderness and that proper rotation of sites is performed. The total number of IMP sc injections and their locations will be recorded for each dosing visit (visits 2 through 4, test or placebo). A 1.5-mL volume from each prefilled syringe must be injected sc for dosing to be considered complete.

5.1.1. Test Investigational Medicinal Product

Fremanezumab is a fully humanized IgG2a/kappa monoclonal antibody derived from a murine precursor. Fremanezumab for CH is being developed for iv and sc administration.

Additional details may be found in [Table 3](#) and in the IB for fremanezumab.

5.1.1.1. Starting Dose and Dose Levels

Patients randomized to receive fremanezumab will receive either 900 mg or 675 mg. At visit 2 (week 0), iv administration of treatment (IMP or placebo) will precede sc administration (IMP or placebo). Patients randomized to the 900-mg iv loading dose group will receive 900 mg of fremanezumab administered via an approximately 1-hour iv infusion followed by placebo as 3 sc injections at visit 2 (week 0) and fremanezumab at 225 mg administered as single sc injections (225 mg/1.5 mL) at visits 3 and 4 (weeks 4 and 8, respectively). Patients randomized to the fremanezumab 675-mg sc quarterly group will receive placebo administered via an approximately 1-hour iv infusion followed by fremanezumab at 675 mg administered as 3 sc injections (225 mg/1.5 mL) at visit 2 (week 0) and placebo administered as single sc injections at visits 3 and 4 (weeks 4 and 8, respectively).

5.1.2. Placebo Investigational Medicinal Product

The placebo will be the same vehicle and excipients as those for fremanezumab. See [Table 3](#) for additional details. Patients randomized to the placebo group will receive placebo administered via an approximately 1-hour iv infusion followed by placebo as 3 sc injections at visit 2 (week 0) and placebo administered as single sc injections at visits 3 and 4 (weeks 4 and 8, respectively).

5.2. Preparation, Handling, Labeling, Storage, and Accountability for Investigational Medicinal Products

Information pertaining to the preparation, handling, labeling, storage, and accountability for the IMP used in this study can be found in [Appendix G](#).

5.3. Justification for Investigational Medicinal Products

5.3.1. Justification for Dose of Test Investigational Medicinal Product

The fremanezumab doses, regimens, and routes of administration to be evaluated in this double-blind, double-dummy, placebo-controlled study were selected on the basis of 3 key factors. First, simulations suggest that C_{max} is the most significant pharmacokinetic parameter in the efficacy of fremanezumab (in migraine). As CH is considered one of the most severe forms of pain a person can experience, treatments that provide quick and lasting relief (ie, for the duration of the cluster period) are a priority for this patient population. Second, the biological nature of the disease mandates the need for any treatment to desensitize the third order neuron, not the second (as is the case in migraine), suggesting that high levels of blockade at the first

neuron would be necessary. Third, the favorable safety profile of the drug, as well as clinical and nonclinical safety data on exposure, suggest that the proposed doses, regimens, and routes of administration will not present any safety concerns.

In the current study, high doses are planned for the first dose (900 mg iv or 675 mg sc) in order to provide a rapid response, especially following iv infusion where higher peak plasma C_{max} generally occur at or shortly after the end of infusion compared with 5 to 7 days postdose for sc injections. The 2 forms of loading dose will provide data to confirm the benefit of either the iv or sc as loading dose. Monthly doses of fremanezumab at 225 mg sc were added to the initial dose of 900 mg iv for maintenance of efficacy. Based on modelling, the inclusion of a loading dose should allow patients to reach steady state faster. The dose of 675 mg sc quarterly in this ECH population will allow for the evaluation of a single treatment dose taking into account the periods of remission seen with this CH form.

